3.7 PRECAUTIONS

3.7.1 Reference Safety Information

For the purpose of reporting AEs and serious adverse events (SAEs):

The Investigator Brochure contains the Reference Safety Information (RSI) for acalabrutinib.

3.7.2 Dietary Restrictions

Acalabrutinib can be taken with or without food. As acalabrutinib is metabolized by CYP3A, subjects should be strongly cautioned against using herbal remedies or dietary supplements (in particular, St John's wort, which is a potent CYP3A inducer). Otherwise, subjects should maintain a normal diet unless modifications are required to manage an AE such as diarrhea, nausea, or vomiting.

3.7.3 Hemorrhage

Serious hemorrhagic events, including fatal events, have occurred in clinical trials with acalabrutinib.

The mechanism for hemorrhage is not well understood. Subjects receiving antithrombotic agents may be at increased risk of hemorrhage. Use caution with antithrombotic agents and consider additional monitoring for signs of bleeding when concomitant use is medically necessary. Consider the benefit-risk of withholding acalabrutinib for at least 3 days pre- and post-surgery. Subjects with hemorrhage should be managed per institutional guidelines with supportive care and diagnostic evaluations as clinically indicated.

3.7.4 Infections

Serious infections (bacterial, viral, and fungal), including fatal events, have occurred in clinical studies with acalabrutinib. The most frequent reported Grade ≥ 3 infection was pneumonia (preferred term).

Consider prophylaxis in subjects who are at increased risk for opportunistic infections. Subjects should be monitored for signs and symptoms of infection and treated as medically appropriate. Refer to [Section 3.7.4.1](#) and [Section 4.1.17](#) for additional information and monitoring guidance for viral hepatitis and [Section 3.7.4.2](#) for additional information and management guidance for signs and symptoms of PML.

3.7.4.1 Hepatitis B Virus Reactivation

Serious or life-threatening reactivation of viral hepatitis may occur in subjects treated with *acalabrutinib*. Therefore, subjects who are hepatitis B core antibody (anti-HBc) positive or have a known history of hepatitis B virus (HBV) infection, should be monitored monthly with a quantitative PCR test for HBV DNA. Monthly monitoring should continue until 12 months after last dose of *acalabrutinib*. Any subject with a rising viral load (above lower limit of detection) should discontinue *acalabrutinib* and have antiviral therapy instituted and a consultation with a physician with expertise in managing hepatitis B. Insufficient data exist regarding the safety of resuming *acalabrutinib* in subjects who develop HBV reactivation.

3.7.4.2 *Progressive Multifocal Leukoencephalopathy*

Cases of progressive multifocal leukoencephalopathy (PML) have occurred in clinical studies with acalabrutinib. Signs and symptoms of PML may include cognitive and behavioral changes, language disturbances, visual disturbances, sensory deficits, weakness, and coordination and gait difficulties.

If PML is suspected, hold further treatment with acalabrutinib treatment until PML is excluded. A diagnostic evaluation may include (but is not limited to):

- Neurologic consultation*
- Brain magnetic resonance imaging (MRI)*
- PCR analysis for John Cunningham virus DNA in cerebrospinal fluid*

If PML is confirmed, permanently discontinue acalabrutinib.

3.7.5 *Cytopenias*

Grade 3 or 4 cytopenias including neutropenia, anemia, and thrombocytopenia have occurred in clinical studies with acalabrutinib. Monitor blood counts as medically appropriate.

Subjects with cytopenias should be managed according to institutional guidelines with maximal supportive care and diagnostic evaluations as clinically indicated. Subjects should be closely monitored as appropriate.

3.7.6 *Second Primary Malignancies*

Second primary malignancies, including solid tumors and skin cancers, have been reported in patients treated with acalabrutinib. The most frequent second primary malignancy was skin cancer (basal cell carcinoma). Subjects should be monitored for signs and symptoms of malignancy. For Subjects who develop a second primary malignancy, subjects should be managed according to institutional guidelines with diagnostic evaluations as clinically indicated, and it may be necessary for subjects to permanently discontinue study treatment. Continuation of acalabrutinib treatment should be discussed with the medical monitor. Please refer to [Section 6.2.3](#) for second primary malignancy reporting guidance.

3.7.7 *Atrial Fibrillation*

Events of atrial fibrillation/flutter have occurred in clinical studies with acalabrutinib particularly in subjects with cardiac risk factors, hypertension, diabetes mellitus, acute infections, or a previous history of atrial fibrillation.

Monitor for symptoms of atrial fibrillation and atrial flutter (e.g., palpitations, dizziness, syncope, chest pain, dyspnea) and obtain an ECG as clinically indicated. Subjects with atrial fibrillation should be managed per institutional guidelines with supportive care and diagnostic evaluations as clinically indicated.

3.7.8 Surgery

Susceptibility to bleeding has been observed with the first generation Btk inhibitor, ibrutinib (IMBRUVICA® package insert). As a precaution, it is suggested that *acalabrutinib* be held for 3 days before and after any major surgical procedure.

3.7.9 Reproductive Toxicity

Definition of Women of Non-reproductive Potential

Women will be considered of non-reproductive potential if they are either:

1) Postmenopausal (defined as at least 12 months with no menses without an alternative medical cause; in women <45 years of age a high follicle stimulating hormone (FSH) level in the post-menopausal range may be used to confirm a post-menopausal state in women not using hormonal contraception or hormonal replacement therapy. In the absence of 12 months of amenorrhea, a single FSH measurement is insufficient.);

OR

2) Have had a hysterectomy and/or bilateral oophorectomy, bilateral salpingectomy or bilateral tubal ligation/occlusion, at least 6 weeks prior to screening;

OR

3) Have a congenital or acquired condition that prevents childbearing.

Highly Effective Methods of Contraception[‡]

Highly effective methods of contraception (to be used during heterosexual activity) are defined as methods that can achieve a failure rate of <1% per year when used consistently and correctly. Such methods include:

- Combined (estrogen and progestogen containing) hormonal contraception associated with inhibition of ovulation, which may be oral, intravaginal, or transdermal*
- Progestogen-only hormonal contraception associated with inhibition of ovulation, which may be oral, injectable, or implantable*
- Intrauterine device (IUD) or intrauterine hormone-releasing system (IUS)*
- Bilateral tubal occlusion*
- Vasectomy of a female subject's male partner (with medical assessment and confirmation of vasectomy surgical success)*

- *Sexual abstinence (only if refraining from heterosexual intercourse during the entire period of risk associated with the study treatments)*

Hormonal contraception may be susceptible to interaction with study or other drugs, which may reduce the efficacy of the contraception method.

Periodic abstinence[†] (eg, calendar, ovulation, sympto-thermal, and post-ovulation methods) and withdrawal (coitus interruptus), spermicides only, and lactational amenorrhoea method (LAM) are not acceptable methods of contraception. Female condom and male condom should not be used together as an effective method of contraception.

[†]Abstinence (relative to heterosexual activity) can only be used as the sole method of contraception if it is consistently employed as the subject's preferred and usual lifestyle and if considered acceptable by local regulatory agencies and IECs/IRBs. Periodic abstinence (eg, calendar, ovulation, sympto-thermal, and post-ovulation methods) and withdrawal are not acceptable methods of contraception.

[‡]If a contraceptive method listed above is restricted by local regulations/guidelines, then it does not qualify as an acceptable method of contraception for subjects participating at sites in this country/region.

Developmental and reproductive toxicology studies in rats have not identified acalabrutinib-related toxicities for fertility, reproductive success, embryofetal development, or embryofetal survival. In rabbits, at dose levels which resulted in maternal toxicities, skeletal variations were associated with reductions in fetal weights. Effects on parturition and post-natal development are pending. For additional details, refer to the Acalabrutinib Investigator Brochure.

Subjects should promptly notify the investigator if they, or their partners, become pregnant during this period. Female subjects must also notify the investigator if they become pregnant within 2 days after the last dose of acalabrutinib. If a female subject becomes pregnant during the treatment period, she must discontinue acalabrutinib immediately. Pregnancy in a female subject or a male subject's partner must be reported as described in [Section 6.2.4](#).

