3.4 SELECTION OF STUDY POPULATION

3.4.1 Inclusion Criteria

Eligible subjects will be considered for inclusion in this study if they meet **all** of the following criteria:

1. Men and women ≥ 18 years of age.
2. Eastern Cooperative Oncology Group (ECOG) performance status of ≤ 2 .
3. Pathologically confirmed de novo ABC DLBCL, and subjects **must have** available archival tissue for central pathology review to be eligible.
4. Relapsed or refractory disease, defined as either: 1) recurrence of disease after a CR, or 2) PR, SD, or progressive disease at completion of the treatment regimen preceding entry to the study (residual disease):
 - Subjects must have previously received a standard anthracycline and rituximab-based first-treatment regimen (eg, R-CHOP).
 - Subjects with suspected residual disease after the treatment regimen directly preceding study enrollment must have biopsy demonstration of residual DLBCL.
 - Subjects who have not received HDT/ASCT must be ineligible for HDT/ASCT as defined by meeting any of the following criteria:
 - Age ≥ 70 years
 - Diffuse lung capacity for carbon monoxide (DLCO) $< 50\%$ by PFT
 - Left ventricular ejection fraction (LVEF) $< 50\%$ by ECHO
 - Other organ dysfunction or comorbidities precluding the use of HDT/ASCT on the basis of unacceptable risk of treatment-related morbidity
 - Subject refusal of HDT/ASCT
 - Subjects who are intolerant to anthracycline-based first-line therapy and meet all other eligibility criteria including recurrent or refractory disease are also eligible.
5. Presence of radiographically measurable lymphadenopathy or extranodal lymphoid malignancy (defined as the presence of ≥ 1 lesion that measures ≥ 2.0 cm in the longest dimension and ≥ 1.0 cm in the longest perpendicular dimension as assessed by CT scan).
6. Agreement to use acceptable forms of contraception during the study and for 30 days after the last dose of study drug if sexually active and able to bear or beget children.

7. Agreement to refrain from sperm donation during the study and for 30 days after the last dose of study drug.
8. Willing and able to participate in all required evaluations and procedures in this study protocol including swallowing capsules without difficulty.
9. Ability to understand the purpose and risks of the study and provide signed and dated informed consent and authorization to use protected health information (in accordance with national and local patient privacy regulations).

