6.2.1 Adverse Event Reporting Period

After the signing of the ICF and prior to the first dose of study drug, all SAEs must be reported. After the first dose of study drug, all AEs/SAEs, irrespective of attribution of causality, must be reported.

All adverse events will be reported until 30 days after the last dose of study drug or the start of new anticancer therapy (whichever comes first). After this period, investigators should report serious adverse events or other adverse events of concern that are believed to be related to prior treatment with study drug.

All SAEs that occur during the reporting period should be followed to resolution or until the Investigator assesses the subject as stable or until the subject is lost to follow-up or withdraws consent. Resolution/stable means the subject has returned to baseline state of health or the investigator does not expect any further improvement or worsening of the event.

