6.2.4 Pregnancy

The investigator should report all pregnancies in study subjects and in the partners of subjects within 24 hours using the Pregnancy Report Form. This form should be faxed or emailed to Acerta Pharma Drug Safety. Any pregnancy-associated SAE must be reported using the SAE report form, according to the usual timelines and directions for SAE reporting ([Section 6.2.5](#)).

Any uncomplicated pregnancy that occurs in a study subject or a partner of a treated subject during this study will be reported for tracking purposes only, if agreed to by the subject or the partner of the subject in this study. All pregnancies and partner pregnancies that are identified during or after this study, wherein the estimated date of conception is determined to have occurred from the time of consent to 30 days after the last dose of study medication will be reported, followed to conclusion, and the outcome reported, as long as the subject or partner is willing to participate in follow-up.

Pregnancy itself is not regarded as an AE unless there is suspicion that the investigational product under study may have interfered with the effectiveness of a contraceptive medication. Likewise, elective abortions without complications are not considered AEs. Any SAEs associated with pregnancy (eg, congenital abnormalities/birth defects/spontaneous miscarriages or any other serious events) must additionally be reported as such using the SAE/Product Complaint form.

Subjects should be instructed to immediately notify the investigator of any pregnancies. Any female subjects receiving *acalabrutinib* who become pregnant must immediately discontinue study drug. The investigator should counsel the subject, discussing any risks of continuing the pregnancy and any possible effects on the fetus.

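### Section 3.7.9 gives women a 2-day post-dose pregnancy notification duty and leaves its general period undefined, which conflicts with the 30-day reporting window and open-ended instruction in Section 6.2.4

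*Protocol*

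**What the plan says.** Section 3.7.9 (Reproductive Toxicity) contains two notification statements. The first is general: "Subjects should promptly notify the investigator if they, or their partners, become pregnant during this period". The paragraph before it concerns animal reproductive toxicology, and nothing in the section says when the period starts or ends. The second is specific to women and carries an explicit limit: "Female subjects must also notify the investigator if they become pregnant within 2 days after the last dose of acalabrutinib". The same paragraph then sends the reader to Section 6.2.4 for how pregnancies in subjects and in male subjects' partners are to be reported.

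Section 6.2.4 (Pregnancy) covers pregnancies in subjects and partners identified during or after the study where "conception is determined to have occurred from the time of consent to 30 days after the last dose of study medication will be reported". These are to be followed to conclusion and the outcome reported, if the subject or partner is willing. The section also says: "Subjects should be instructed to immediately notify the investigator of any pregnancies". That instruction has no time limit.

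Two other post-dose windows stand in the protocol. Inclusion criterion 6 in Section 3.4.1, repeated in the synopsis, requires "Agreement to use acceptable forms of contraception during the study and for 30 days after the last dose of study drug", for those who are sexually active and able to have children. Section 6.2.1 says "All adverse events will be reported until 30 days after the last dose of study drug", or until new anticancer therapy starts if that comes first.

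**The concern.** The investigator's reporting duty depends largely on what subjects and their partners disclose. A notification duty that ends earlier than the reporting window it feeds is therefore a weak link. Here the one notification statement with an explicit post-dose limit, worded as an obligation, is much shorter than the window in which pregnancies are reportable. It also applies to women alone. For partners of male subjects, 3.7.9 gives no defined post-dose period at all, although 6.2.4 treats their pregnancies in the same way as those of subjects.

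What is at stake is the capture of pregnancy-exposure data. The primary objective is the safety profile, and 3.7.9 itself notes that some reproductive-toxicology results are still outstanding. Adverse event collection is not a substitute, because under 6.2.4 a pregnancy is not ordinarily an adverse event.

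**Working it through.** The protocol states no derived figure to reproduce, so the check compares the time windows.

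**Windows as stated**

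| Source | Who | What | Post-dose limit |
|---|---|---|---|
| 3.7.9, general sentence | Subjects and partners | Notify the investigator | Undefined |
| 3.7.9, specific sentence | Female subjects | Notify the investigator | 2 days |
| 6.2.4, reporting | Subjects and partners | Report, follow, give outcome | Conception up to 30 days |
| 6.2.4, instruction | Subjects | Notify any pregnancy | None |
| 3.4.1, criterion 6 | Subjects | Contraception | 30 days |

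**Step 1: the stated limits.** 30 − 2 = 28 days. A conception on days 3 to 30 after the last dose is reportable under 6.2.4 but lies beyond the explicit limit for women in 3.7.9. This is a count of calendar days for one sentence of 3.7.9. It does not estimate missed pregnancies.

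**Step 2: whether the general sentence in 3.7.9 closes the gap.** If its undefined period already ran to 30 days after the last dose, the 2-day sentence would add nothing. The 2-day sentence is worded as an addition to the general one, which suggests that the general period ends at or near the last dose and that the 2 days extend it. The text does not settle this, so the general sentence cannot be relied on to cover days 3 to 30. For partners it is the only notification sentence in 3.7.9, so their post-dose period is undefined.

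**Step 3: whether 6.2.4 closes the gap.** Its instruction to notify any pregnancy does cover days 3 to 30. It leaves the 2-day sentence in force, however, so sites hold three versions of the duty: unlimited, undefined and 2 days.

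**Step 4: whether scheduled testing closes the gap.** Appendix 4 has a urine pregnancy test at the early termination/safety follow-up visit. Section 4.3 places the safety follow-up at 30 (±7) days, that is, from 30 − 7 = day 23 to 30 + 7 = day 37.
- A visit on day 23 precedes the last 7 days of the reporting window (days 24 to 30).
- A test on or near the visit date may be too early to detect a conception shortly before it.
- The safety visit is not required if another anticancer therapy has started.
- The test is for women of childbearing potential, so it does not cover partners.
- The long-term follow-up column of Appendix 4 schedules no further pregnancy test.

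**Result.** The 6.2.4 instruction and the test make a missed case less likely. Neither removes the conflict in the text.

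**The case against.** The strongest reply is that no post-dose day lacks a notification instruction once the protocol is read as a whole. Section 6.2.4 asks that subjects be told to notify any pregnancy, and 3.7.9 sends the reader to 6.2.4. The 2-day sentence adds a duty; it nowhere says that later pregnancies need not be mentioned. There is a second route of detection in the follow-up pregnancy test, and subjects who stop treatment stay in follow-up under Sections 3.8 and 4.4. Criterion 6 concerns contraception, so its length does not by itself contradict a notification sentence. What subjects are actually told is in the consent form, which is not available here.

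Much of this stands. A reader might infer from 3.7.9 that women need notify no pregnancy after day 2, or that the 28 days computed above fall outside every notification duty. The protocol does not support either reading, because the 6.2.4 instruction reaches those days. Nor can it be said that the consent form repeats the 2-day limit. Criterion 6 is a consistency check; the conflict itself is between 3.7.9 and 6.2.4.

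The reply does not explain why the only explicit post-dose notification limit is shorter than the reporting window, and it supplies neither the missing definition nor a stated post-dose period for partners. The cross-reference in 3.7.9 concerns how a pregnancy is reported; it does not reset when the subject must disclose it.

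**Conclusion.** The notification passages conflict and are wrong as written. Section 3.7.9 sets a 2-day limit for women, an undefined period for subjects generally, and no defined post-dose period for partners. Section 6.2.4 sets a 30-day conception window for reporting and an unlimited instruction to notify. A site or subject who follows the explicit 2-day sentence could leave a reportable pregnancy conceived on days 3 to 30 unnotified.

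The practical size is modest. The study plans 20 subjects, the protocol gives no expected number of pregnancies, and none is estimated here. The effect is confined to safety-data capture and consistency of the text; sample size, endpoints and analysis sets are untouched. The conclusion rests on the current protocol text and on the assumption that at least some sites or subjects would work from 3.7.9 without applying the broader instruction in 6.2.4. It is worth correcting because the correction is simple and the data concerned are ones the protocol undertakes to collect. It does not depend on which period is clinically appropriate, and no view is taken on that.

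**What to change.** Reconcile Sections 3.7.9 and 6.2.4:

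- Define the period in the general notification sentence of 3.7.9, with a start and an end.
- Make the notification duty cover the same days as the reporting window in 6.2.4, for female subjects and for partners of male subjects, and reconcile the 2-day sentence with it.
- Check that the result is consistent with the contraception period in inclusion criterion 6 (Section 3.4.1 and synopsis) and with the wording of the consent form.

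The choice of period is for the sponsor's clinical and safety functions. The cost is a few lines in a protocol amendment, a check of the consent form and a short note to sites. No new visit, test or analysis is needed.

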3.7.10 Overdose Instructions

In the event of ingestion of more than the recommended dosage per protocol, additional clinical monitoring is recommended by the sponsor. For any subject experiencing an acalabrutinib overdose, observation for any symptomatic side effects should be instituted,

and vital signs and biochemical and hematologic parameters should be followed closely (consistent with the protocol or more frequently, as needed). Appropriate supportive management to mitigate adverse effects should be initiated. If the overdose ingestion is recent and substantial, and if there are no medical contraindications, use of gastric lavage or induction of emesis may be considered.

The Acerta Pharma medical monitor should be contacted if a study drug overdose occurs.

3.8 STOPPING RULES

All study participants may receive *acalabrutinib* indefinitely as long as they are safely benefitting. However:

- Any subject has the right to withdraw from the study at any time.
- Any subject who has objective evidence of definitive DLBCL progression while receiving study treatment at the highest individual tolerable dose level allowed in the protocol (see [Section 3.5.5](#)) should be withdrawn from the study treatment. Note: If there is uncertainty regarding whether there is DLBCL progression, the subject should continue study treatment and remain under close observation (eg, evaluated at 4- to 8-week intervals) pending confirmation of progression. In particular, transient worsening of disease during temporary interruption of study therapy (eg, for intercurrent illness, drug-related toxicity, or surgery) may not indicate disease progression. In such circumstances, and if medically appropriate, subjects may resume therapy and relevant clinical, laboratory, and/or radiographic assessment should be done to document whether tumor control can be maintained or whether actual disease progression has occurred.
- Any subject who is unable to tolerate rechallenge with the lowest protocol-described, dose-modified levels (see [Section 3.5.5](#)) should be withdrawn from the study treatment unless continued therapy is permitted by the Acerta Pharma medical monitor.
- Any subject whose medical condition substantially changes after entering the study should be carefully evaluated by the investigator in consultation with the Acerta Pharma medical monitor. Such subjects should be withdrawn from study treatment if continuing would place them at risk.
- Any subject who becomes pregnant or begins breastfeeding should be removed from study treatment.
- Any subject who becomes significantly noncompliant with study drug administration, study procedures, or study requirements should be withdrawn from study treatment in

circumstances that increase risk or substantially compromise the interpretation of study results.

- The investigator, in consultation with the Acerta Pharma medical monitor, may withdraw any subject from the study treatment, if, in the investigator's opinion, it is not in the subject's best interest to continue.

Subjects who discontinue study therapy will continue on study for safety ([Section 4.3](#)) and time-to-next therapy ([Section 4.4](#)) unless they withdraw consent for further follow-up.

Thus, all subjects receiving ≥ 1 dose of study drug will be followed during the immediate post-therapy and long-term follow-up assessments unless the subject withdraws consent for such follow-up to be conducted or enrolls in an *acalabrutinib* maintenance study. The date the subject is withdrawn from study treatment or from the study (including long-term follow-up) and the reason for discontinuation will be recorded and also should be described on the appropriate eCRF.

